4.0 General Approach

Our approach will be to gather data on vascular (including blood pressure, augmentation index, vascular stiffness, endothelial function), inflammation (including DAS28, IL-17, IL-6, TNF- α), metabolic (including insulin, glucose, catecholamines), microbiome (stool and saliva), oxidative stress (F2 isoprostanes excretion), and tissue Na^+ measures after, a high-salt and low-salt intake each administered for 8 weeks, in random order, in a crossover study with a 4-week washout period between high-salt and low-salt diets in 22 patients with moderately active RA. It is not possible to blind patients to diet - thus patients and the dietitian will know whether a diet is high-salt (HS) or low-salt (LS). However, we will ensure that investigators performing assessments are blind to the dietary intervention.

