During the in-person screening, weight, waist and hip circumference, and blood pressure will be measured. Joints will be examined for swelling and tenderness. Study staff will review directions on collection of 24-hour urine, stool collection, and blood pressure monitoring. Participants will be provided a kit containing containers for urine and stool collection and an at-home blood pressure monitor for participants to measure their blood pressure weekly for the duration of their participation in the study. An insulated bag will be provided to transport materials to VUMC at each study visit. Kit contents will be replaced at each visit. The at-home blood pressure monitor will be returned to study personnel at the end of the study to be cleaned.

During the in-person screening, patients who have not had a complete blood count (CBC), AST, ALT, alkaline phosphatase, and creatinine performed in the previous 3 months will have a blood sample drawn for these tests to exclude serious co-morbidity. Women of childbearing potential will have a urine test performed to exclude pregnancy at each visit.

c. Patients will be asked to weigh themselves once a week and the same time of day and to report that weight to the study staff. Weight will be measured at each visit. **Procedures for Visits (the following procedures will be performed at visits noted)**

1. Disease Activity (all visits)

At each visit we will assess a RA disease activity (DAS 28 score) by joint examination and questionnaire as previously described.¹⁹

2. Blood and urine collection (all visits)

Sample collection: The day before each visit patients will collect a 24-hour urine specimen. At each visit we will also obtain a urine sample and draw venous blood for laboratory testing. An aliquot of the 24-hour urine sample will be frozen and stored for later assays that will include electrolyte and creatinine levels to assess compliance with the diet. An aliquot of the urine sample collected at the

study visit will be frozen and stored for later assays that will include F2-isoprostane measurements. Venous blood will be drawn for measurement of hsCRP, ESR, glucose, insulin, and inflammatory mediators including IL-17, IL-6, and TNF- α as we have previously described^{16,17,18}.

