7.0 Side effects

At every visit study personnel will enquire about adverse effects in a standardized manner, though there is no intervention other than diet. In the event of a positive response, the adverse effect will be assessed by the investigator and the likelihood of a causal relationship with HS/LS diets (definitely, probably, uncertain, probably not, definitely not) and regarding its severity (mild, moderate, severe). Patients who develop serious adverse events causally related to participation in the study will be discontinued from the study.

- a. **Side effects of salt supplements and study procedures:** Salt is a naturally occurring compound found in most food products. No side effects have been reported from salt intake, however salt could cause nausea. The amounts being administered for the study will be within safe levels determined from previous similar studies and the general population intake. A high-salt diet may increase blood pressure in some people. We will provide patients with a home blood pressure monitor so that they can take their blood pressure at home once a week and ask them to call us if it is greater than 160/100 mm Hg. Venipuncture may cause bleeding or bruising. The automatic inflation of the arm cuff for ambulatory blood pressure monitoring could disturb sleep. MRI: There are no known major

risks with an MRI scan; but, it is possible that harmful effects could be found in the future. Even though the tunnel is open, it may bother some patients (claustrophobia), and they hear the noise made by the magnet during the scan. We provide earplugs to reduce the noise. Metal pieces in the body could move during the scan and damage nearby tissues or organs. Patients will not be able to have this scan if they have a non-MRI safe device implanted such as an aneurysm clip in the brain, a heart pacemaker or defibrillator or a cochlear implant. They also may not be able to have this scan if they have iron-based tattoos or pieces of metal (bullet, BB, shrapnel) close to or in an important organ (such as the eye). We will exclude pregnancy by performing a urine test prior to the MRI. Certain metal objects like watches, credit cards, hairpins, writing pens, etc. may be damaged by the machine or may be pulled away from the body during the scan. For these reasons, patients are asked to remove these objects before going into the room for the scan.

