10.0 Statistical Methods

a. Sample Size

We will plan to enroll 50 RA patients assuming that many will drop out. The sample size estimation of n=18 was based on two outcomes of major interest: the comparison of the change from baseline for 1) DAS 28 and 2) Skin Na⁺ concentrations using a paired t-test comparing post-treatment values after receiving HS or LS diet. However, in the actual data analysis, we will compare the change from baseline to post-treatment value between the two treatment phases (i.e., linear mixed effect models) which will improve power, thus the sample size analyses presented is the most conservative. Sample size was estimated using PS-Power for a paired t-test with a 2-sided test at a significance level of 5%. Assuming that less than 20% of subjects will dropout or have incomplete data is a reasonable assumption based on our previous studies. If the number of dropouts exceeds our estimate we will replace them. For patients who are withdrawn or lost to follow-up without data for week 8 for either arm, an intention-to-treat approach will be applied. For inflammation (DAS28 score) a sample size of 18 patients will provide 95% power to detect a difference between HS and LS arms of 1.0 unit – a clinically meaningful reduction. For Skin Na⁺ measurements the standard deviation (SD) is approximately 5.0 mmol/L and a difference between groups of this magnitude represents a clinically important difference. A sample size of 18 patients will provide ~98% power to detect a difference in skin Na⁺ of 5 mmol/L, respectively. For secondary outcomes measures (e.g., inflammation (e.g., CRP, IL-6, T cell populations) and vascular function (e.g., 24 h BP) we have >95% power to detect a difference between groups equivalent to 1 SD – a difference likely to clinically relevant.

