12.0 Statistical Analysis

Baseline characteristics will be summarized for patients who are randomized to the two treatments (HS vs. LS) at baseline. A crossover design eliminates confounding due to uneven distribution of baseline variables because a patient serves as his/her own control, thus a complete balance in baseline data is obtained in the absence of dropouts.

The outcomes of interest are the comparison of the change in blood pressure, vascular stiffness (Aix, PWV), endothelial function (PAT), insulin resistance (HOMA), skin Na^+ concentrations, and inflammation (DAS28 score) between baseline and 1) after 8 weeks of HS diet, 2) after 8 weeks of LS diet. We will use Analysis of Covariance (ANCOVA) which is a form of multiple linear regression model including the blood pressure at the end of each treatment (HS and LS) or the last observation for patients with early withdrawal as an outcome variable, group variable (HS or LS) as a main independent variable, and baseline blood pressure as a covariate. By including the baseline value as a covariate, the regression coefficient for the group (HS or LS) becomes the between-group (HS vs LS) difference in the change in blood pressure response. This method is often superior to the method that used the change in blood pressure directly as the outcome variable (such as student's t-test for the change) because it adjusts for baseline differences as a covariate which reduces measurement errors more effectively.

A similar approach will be used for the vascular stiffness (Aix, PWV), endothelial function (PAT), insulin resistance (HOMA), and inflammation (DAS28 score) and skin Na^+ concentrations.

If unequal distribution of some of the variables is detected by the univariate analyses of baseline characteristics between groups, those variable will be included in a multiple linear-regression model in addition to a set of a prior chosen covariates based on clinical relevance such as age, sex, and race, with knowledge of not overfitting the model

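### DAS28 is the only inflammation outcome named in Section 12.0, yet part of it comes from patients who know their diet; the swollen-joint count and hsCRP/ESR need a model and a role in the conclusion

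*Combined protocol and SAP*

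**What the plan says.** Section 4.0 accepts that the diet cannot be masked from patients: "thus patients and the dietitian will know whether a diet is high-salt (HS) or low-salt (LS". It adds a commitment about the assessors: "we will ensure that investigators performing assessments are blind to the dietary intervention".

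Section 6.0, c.1 describes the disease-activity measure: "At each visit we will assess a RA disease activity (DAS 28 score) by joint examination and questionnaire as previously described". The same section provides for hsCRP, ESR and inflammatory mediators from blood drawn at all visits, and Table 1.A marks joint count, hsCRP and ESR at visits 1 to 4.

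Section 12.0 lists the outcomes to be analysed and ends the list with "skin Na^+ concentrations, and inflammation (DAS28 score) between baseline" and the end of each diet. When it extends the ANCOVA to outcomes other than blood pressure, it again writes "insulin resistance (HOMA), and inflammation (DAS28 score". It names no other inflammation measure.

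Section 10.0 does mention others: "For secondary outcomes measures (e.g., inflammation (e.g., CRP, IL-6, T cell populations". It claims more than 95% power for these at a difference of 1 SD. It also makes DAS28 one of the two outcomes behind the sample size of 18.

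**The concern.** Hypothesis 1 in Section 3.0 is directional: less sodium, less inflammation. As Section 12.0 stands, the evidence for it is a difference in DAS28. Part of that score is what the patient writes on a questionnaire, and part depends on whether the patient says a joint hurts when it is examined. Both come from someone who knows which diet they have just eaten for about eight weeks. A blind examiner cannot remove expectation from the patient's own answers.

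At stake is the meaning of a positive result. A diet difference carried entirely by tenderness and self-rating would be reported as reduced inflammation, even if swelling and the laboratory markers had not moved. The measures that could tell the two explanations apart are already collected, but the analysis section does not use them. If they are brought in after the DAS28 result is known, their selection will look post hoc.

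**Working it through.** **Which parts of the score are exposed**

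- Questionnaire: completed by the unmasked patient. Examiner blinding gives no protection.
- Tender joints: elicited and recorded by a blind examiner, but dependent on the patient's response. Partly protected.
- Swollen joints: judged by the examiner. Protected to the extent that the blinding in Section 4.0 holds.
- ESR and hsCRP: laboratory values, not open to biased reporting by the patient.

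The documents do not state the DAS28 version or its components. The reference cited for the method (number 19) is listed as RA classification criteria. The patient-reported share of the score therefore cannot be derived from the documents.

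**Inputs (Section 10.0)**

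Paired t-test, two-sided 5%, n = 18. DAS28: difference 1.0, power 95%, no SD given. Skin Na+: SD about 5.0, difference 5 mmol/L, power about 98%.

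**Formula**

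Power = P(|T| > t(0.975, n−1)), where T is noncentral t with n−1 degrees of freedom and noncentrality (difference / SD_d) × √n. SD_d is the SD of the paired differences.

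1. *Reproduce the plan's figure that can be checked.* Skin Na+, reading 5.0 as SD_d: 5/5 = 1, n = 18, power 97.9%. This agrees with the stated 98%, so the method matches.
2. *Solve for the missing DAS28 SD.* Power of 95% at n = 18 needs difference / SD_d = 0.902, so SD_d = 1.0 / 0.902 = 1.11.
3. *Smallest significant difference.* t(0.975, 17) × SD_d / √18 = 2.110 × 1.108 / 4.243 = 0.55 units, about half of the 1.0 unit planned for.
4. *No diet effect, reporting bias b.* Put b in place of the difference. The chance of p < 0.05 is 6.5% at b = 0.1, 11.2% at 0.2, 19.2% at 0.3, 30.4% at 0.4 and 43.9% at 0.5. At b = 0 it is 5%.
5. *Sensitivity to SD_d (n = 18).*

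| SD_d | Significant from | b = 0.2 | b = 0.5 |
|---|---|---|---|
| 0.8 | 0.40 units | 17.0% | 70.5% |
| 1.11 | 0.55 units | 11.2% | 43.9% |
| 1.5 | 0.75 units | 8.3% | 26.6% |

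6. *Sensitivity to n (SD_d = 1.11).* The threshold falls to 0.49 units with 22 completers and 0.31 with 50. At 50 completers, b = 0.2 gives significance 24.0% of the time and b = 0.5 gives 87.9%. A larger sample makes a fixed bias easier to detect; it does not remove it.
7. *Would agreement in direction be enough?* With no true effect, at least one of two independent markers moves in the favoured direction with probability 1 − 0.5² = 75%, and one of three with 1 − 0.5³ = 87.5%. Such a rule would pass most spurious results, so the supporting measures must be judged on size and precision.

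**The case against.** The strongest reply is that open diet is unavoidable, the protocol says so, and it commits to blind assessors. Objective markers are collected at all four study visits, and Section 10.0 already calls CRP and IL-6 secondary inflammation outcomes. Blinding also gives some protection to the tender count, because it removes the examiner's influence on how tenderness is elicited and scored. Section 11.0 describes a pilot study, and nothing in the documents shows that expectation bias is large. All of this stands. It narrows the point to what Section 12.0 leaves out: a model for those markers and a rule for reading DAS28 beside them.

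Four stronger readings are tempting, and the documents do not support them.

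- *The plan has no objective inflammation outcome.* This is true only of the list in Section 12.0. Section 10.0 names several.
- *The adverse-effect procedure breaks the examiner's blinding.* Section 7.0 says "At every visit study personnel will enquire about adverse effects in a standardized manner" and then that "the adverse effect will be assessed by the investigator and the likelihood of a causal relationship with HS/LS diets" is rated. It does not say that either person performs the joint examination, and causality can be rated without knowing which diet the patient is on. Silence on role separation does not contradict the explicit commitment in Section 4.0.
- *Patients have been told that low salt helps RA.* The consent text is not available, so what they were told is unknown. The point needs only that they know their diet.
- *Expectation would supply a given share of the 1.0 unit.* With no components, baseline values or bias size in the documents, any such share is an assumption.

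**Conclusion.** The point holds. As written, Section 12.0 allows a shift in patient-reported items to stand as support for Hypothesis 1. That conclusion rests on the text alone: patients know their diet, DAS28 draws partly on their answers, and no other inflammation measure has a stated analysis there.

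The size is illustrative. It assumes no true diet effect, the paired t-test of Section 10.0 (not the ANCOVA of Section 12.0), 18 completers, and an SD of paired differences back-calculated from the stated power. On that basis about 0.55 units reaches significance, and an assumed bias of 0.2 to 0.5 units would do so about 11% to 44% of the time. Over SDs of 0.8 to 1.5 the range is about 8% to 71%. The documents cannot show whether a bias of that order will occur. This is a worthwhile, inexpensive improvement to the analysis plan; it does not show that the trial is invalid or that its blinding has failed.

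**What to change.** **Section 12.0, analysis.** Add the swollen-joint count and hsCRP/ESR as prespecified inflammation outcomes, analysed by the same model as DAS28. Report their estimates and 95% confidence intervals beside DAS28, together with the tender-joint count and the patient-reported item. This requires the DAS28 components to be listed.

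**Section 12.0, interpretation.** State in advance that the conclusion on Hypothesis 1 rests on the size and confidence intervals of the measures less open to expectation, and not on agreement in direction alone. A DAS28 difference carried only by tenderness and the patient-reported item is to be reported as a change in patient-reported disease activity. If the intervals for swelling and hsCRP/ESR are wide, the finding on inflammation is inconclusive.

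**Section 6.0, c.1.** To support the blinding promised in Section 4.0, have the joint count completed before the adverse-effect enquiry, and instruct patients not to mention their diet to the examiner. There is no need to bar the examiner from judging causality; that might require extra staff, and the documents do not describe staffing.

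**Cost.** No new measurement, provided that the swollen count, tender count and patient-reported item are stored separately. The change is wording and visit order. The downside is a few extra reported analyses and a more cautious conclusion if the components disagree.

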3.0 Hypothesis

In this study we propose to address the following hypotheses: 1) Reduction in dietary sodium will decrease inflammation in patients with RA. 2) Reduction in dietary sodium will decrease blood pressure in patients with RA. 3) Reduction in dietary sodium will decrease tissue Na^+ in patients with RA.

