High-salt intake adversely affects endothelial function and leads to vascular stiffness^{7,8,11}. To determine the effects of high-salt intake on endothelial function and vascular stiffness in RA, we will measure augmentation index (AiX) and pulse wave velocity (PWV) at each visit. Subjects will undergo non-invasive pulse-wave analysis using the commercially available SphygmoCor system (AtCor Medical, Sydney, Australia). This system uses a transfer function to calculate central arterial pressure from measurements obtained at the radial artery by a hand-held tonometer (Millar pressure tonometer, PWV Medical, Sydney, Australia). After at least 10 minutes of supine rest, peripheral blood pressure will be measured twice using an automated sphygmomanometer (Dinamap Pro 110, GE Healthcare, WI, USA) and augmentation index, aortic (carotid to femoral) pulse-wave velocity (PWV) and brachial (carotid to radial) PWV will be determined using applanation tonometry. The tonometer will be held at the point of maximal pulsation and pressed lightly against each respective artery (i.e., radial, carotid, and femoral arteries.) Measurements are recorded after at least 12 consecutive beats, and the quality of the waveforms confirmed by the quality control function provided by the software. Since augmentation index is influenced by heart rate, an index normalized for a heart rate of 75 beats per minute is used.

Endothelial function will be measured using peripheral arterial tonometry (PAT), a finger plethysmographic device allowing isolated detection of pulsatile arterial volume changes will also be used to assess endothelial function in relation to the salt diet. This device (Itamar Medical Ltd., Caesarea, Israel) consists of two finger-mounted probes, which include a system of inflatable latex

air-cushions within a rigid external case. The probe design allows the application of a constant and evenly distributed near-diastolic counterpressure within the entire probe, which increases sensitivity by unloading arterial wall tension, and prevents venous blood pooling to avoid venoarteriolar reflex vasoconstriction. Pulsatile volume changes of the fingertip are sensed by a pressure transducer and transferred to a personal computer where the signal is processed and stored. The change in flow post-occlusion reflects endothelial function.

5. MRI measurement of tissue Na⁺ content (visits 2 and 4)

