Each subject will have two MRIs. These will be performed at the end of the low-salt and high-salt phases. We will quantify Na⁺ content in skin and muscle by ²³Na MRI using a 3.0 T Phillips Achieva scanner, equipped with a ²³Na coil. Scans will be performed in the Vanderbilt University Institute of Imaging Science. This will take about an hour. Urine pregnancy testing will be performed before the MRI in women of childbearing potential. The MRI will be scheduled on the same days as visits 2 and 4 if possible; however, it is possible that for logistic reasons this may not always be possible and the MRI and in that case the MRI and clinical visits will occur on different days.

6. Microbiome specimen collection (all visits)

Stool and oral microbiota samples will be obtained from participants at each study visit. Microbiota specimens will be used to examine the relationship between microbiota and disease characteristics as well as responses to salt and will be stored for future studies.

Stool collection: Stool from a single bowel movement will be collected by the subject before each study visit. Subjects will be provided with instructions and a materials kit for collecting stool prior to the study visit. Subjects will bring collected stool to the study visit. Stool will be collected within 24 hours before the study visit and will be kept at room temperature.

Oral microbiota collection: Subjects will be asked to not brush or floss teeth within 12 hours of the scheduled assessment. Subjects will be asked to spit into a sterile container. Approximately 5 ml of saliva will be collected and frozen at each study visit.

Table 1.A Procedures and Labs - Study Summary

Procedure/Lab	Screen, virtual* *	Screen, in person	Visit 1 Baseline #1	Visit 2 HS/LS	Visit 3 Baseline #2	Visit 4 HS/LS
History	+		+	+	+	+
Exam		+	+	+	+	+

Joint Count	Self report	+	+	+	+	+
Disease activity			+	+	+	+
Aug Index			+	+	+	+
PWV			+	+	+	+
PAT			+	+	+	+
24-hr Blood pressure			+	+	+	+
Na+ MRI				+		+
CBC		+*				
ALT, AST, creatinine		+*				
Insulin			+	+	+	+
Glucose			+	+	+	+
hsCRP			+	+	+	+
ESR			+	+	+	+
Plasma			+	+	+	+
Serum			+	+	+	+
24-hr Urine			+	+	+	+
DNA/RNA			+			
Stool			+	+	+	+
Saliva			+	+	+	+
Pregnancy testing, urine		+	+	+	+	+

*Labs only drawn at in-person screening if not available from previous 12 weeks.

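### Skin Na+ is assigned a change-from-baseline analysis with a baseline covariate, but no baseline Na+ MRI is scheduled and the plan does not say what replaces it

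*Combined protocol and SAP*

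**What the plan says.** Section 3.0 gives as its third hypothesis: "Reduction in dietary sodium will decrease tissue Na^+ in patients with RA". Section 6.0 c.5 says that Na+ "content in skin and muscle by" MRI will be quantified.

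Section 10.0 a names skin Na+ as one of two outcomes that drive the sample size. It describes them as "the comparison of the change from baseline for 1) DAS 28 and 2) Skin" Na+ and, in the same sentence, gives the sizing test as one "using a paired t-test comparing post-treatment values after receiving HS or LS diet". It then says that in the data analysis itself "we will compare the change from baseline to post-treatment value between the two treatment phases (i.e., linear mixed effect models". The section credits this with more power and on that ground calls the sizing conservative.

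Section 12.0 includes skin Na+ among the outcomes whose change is taken from baseline to the end of each 8-week diet. It sets out an ANCOVA for blood pressure, with the end-of-diet value as response, diet as the main factor and the baseline value as covariate. It then extends a similar approach to skin Na+.

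On scan timing, Section 6.0 c.5 says: "Each subject will have two MRIs. These will be performed at the end of the low-salt and high-salt phases". Its heading restricts the MRI to visits 2 and 4. In Table 1.A the Na+ MRI row is marked at those two visits and is empty under the first baseline visit and under "Visit 3 Baseline #2".

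Section 11.0 applies last observation carried forward to patients who withdraw after randomization. Another sentence there excludes a patient's data for a phase without follow-up data.

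**The concern.** The analysis written for a sizing outcome calls for data that the visit schedule does not produce. The analyst will have to choose a replacement, and the plan gives no rule for that choice, so it could be made after the data are seen. The plan does name one comparison that needs only the two scans, the paired test of post-treatment values. It presents this as the sizing test, however, and then says that the data analysis will do something else.

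Two further things are at stake. The reassurance that the planned analysis is more powerful than the sizing test rests, for skin Na+, on baseline values that will not exist. And with only two scans, one on each diet, the only scan that could be carried forward to replace a missing visit 4 scan was taken on the opposite diet.

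**Working it through.** **Step 1. What each analysis needs, against what is scheduled.** Visits 1 and 3 are the baselines for the first and second diet, and visits 2 and 4 are the ends of the diets (Section 6.0 a and Table 1.A).

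| Outcome listed in Section 12.0 | Visit 1 (baseline) | Visit 2 (end of diet) | Visit 3 (baseline) | Visit 4 (end of diet) |
|---|---|---|---|---|
| 24-hour blood pressure | yes | yes | yes | yes |
| Augmentation index, PWV | yes | yes | yes | yes |
| PAT | yes | yes | yes | yes |
| Insulin and glucose (HOMA) | yes | yes | yes | yes |
| DAS28 | yes | yes | yes | yes |
| Skin Na+ (MRI) | **no** | yes | **no** | yes |

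Baseline values per patient: 0 of 2 for skin Na+, and 2 of 2 for every other outcome.

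**Step 2. What can be formed for skin Na+.**
- Change score (end-of-diet value minus that phase's baseline): it needs visits 1 and 3, so it cannot be formed in either phase.
- Baseline covariate in the ANCOVA: it needs the same values, so it is not available.
- End-of-diet response in the ANCOVA: available from visits 2 and 4.
- Within-patient difference, D = end-of-HS value minus end-of-LS value: available for every patient with both scans.

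The visit 2 scan cannot stand in as the second-phase baseline. It is the outcome of the first diet and precedes the 4-week washout. No other source of skin Na+ is described.

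**Step 3. The plan's own power figure.** Inputs from Section 10.0 a: n = 18, difference 5 mmol/L, SD 5.0 mmol/L, paired t-test, two-sided 5%. The SD is taken here as that of D.
- Noncentrality = (5 / 5.0) × √18 = 4.243
- Degrees of freedom = 18 − 1 = 17
- Power from the noncentral t distribution = 97.9%, against a stated figure of about 98%

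The figure is reproduced. This test uses only D, which the two scheduled scans supply, so the missing baselines leave it unchanged.

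**Step 4. The claimed gain in power.** Section 10.0 compares the sizing test with an analysis of changes from baseline. For skin Na+ the second of these cannot be computed, so no gain from using the baseline can be realised.

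**Step 5. Carry-forward.** Take a patient on HS first who has a visit 2 scan and no visit 4 scan. Carrying the last scan forward sets the LS value equal to the HS value, so D = HS − HS = 0. The reverse order gives the same result. The other Section 12.0 outcomes also have a visit 3 value; for skin Na+ the visit 2 scan is the only value there is to carry.

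**The case against.** The strongest reply is that little is broken. The aim is a low-salt versus high-salt comparison, which two end-of-diet scans answer within each patient. The sizing sentence names a test that these scans support. The ANCOVA response is the end-of-diet value, which exists, and skin Na+ is promised a similar approach, not an identical one. A mixed model could also improve slightly on the paired t-test without any baseline, by using patients who have only one scan.

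Much of this stands, and it limits the point. A reader might infer that the skin Na+ hypothesis cannot be tested, that the trial is underpowered for it, or that nothing in the Section 12.0 model can be fitted. The documents do not support any of these: the contrast is estimable, the power figure is reproduced, and only the baseline term and the change score are missing. Nor can one say that a mixed model offers no gain of any kind. What is lost is the gain that Section 10.0 ties to the change-from-baseline comparison.

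The reply does not remove the mismatch. Sections 10.0 and 12.0 both put skin Na+ on a baseline footing. A similar approach does not say what takes the place of the missing term, and the one comparison that fits the data is the one set aside for the actual analysis.

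On carry-forward, a reader might infer a known bias toward no difference. That is not supported either. Section 11.0 can be read as excluding the missing phase. Section 5.0 e provides an exit visit after a flare, without stating its content, and Section 10.0 allows replacement if dropouts exceed the estimate. The documents also give no count of patients scanned at visit 2 but not at visit 4.

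**Conclusion.** The point holds in this limited form. For skin Na+, and for no other outcome listed in Section 12.0, the planned change score and baseline covariate cannot be formed, because 0 of 2 baseline scans are scheduled, and the plan does not name a replacement. This is an analysis that is wrong as written for a sizing outcome, not merely a missing detail. The heading, the text and the table on scan timing all agree, so it is not a misprint in one place.

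For skin Na+, the conclusion that the sizing is conservative is unsupported so far as it rests on the change-from-baseline comparison. The sample size of 18 is not disputed. The power of 97.9% assumes that 5.0 mmol/L is the SD of the within-patient difference; the documents do not say so, but that reading reproduces their figure. Carry-forward across diets is a secondary consequence that needs a clear rule, and no size of bias is claimed for it.

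**What to change.** - **Sections 10.0 and 12.0:** exempt tissue Na+ from the change-from-baseline and baseline-covariate wording. State that it is analysed as the within-patient HS minus LS difference in end-of-diet values, by a paired comparison or by a mixed model with diet, period and a patient effect. This matches the comparison used for sizing.
- **Section 10.0:** limit the statement about improved power and conservative sizing to outcomes that are measured at baseline.
- **Section 11.0:** state that a visit 2 scan, taken on the opposite diet, is not carried forward into a missing visit 4 scan.

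The cost is wording only, with no added scan, visit or patient.
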